# **ABBREVIATIONS**

**ABG** = Arterial blood gas **AKI** = Acute Kidney Injury **ALI** = Acute Lung Injury **ALT** = Alanine transaminase **APACHE**=Acute physiologic and chronic health evaluation **ARDS** = Acute Respiratory Distress Syndrome **AST** = Aspartate aminotransferase **AUC**= Area under the curve **AUDIT**= Alcohol Use Disorders Identification Test **BIPAP**= Bi-level Positive Airway Pressure **BMI** = Body Mass Index **CCC** = Clinical Coordinating Center **CK** = Creatinine Kinase **CLP**=Cecal ligation and puncture **CTPA/V** = Computerized Thoracic Pulmonary Angiography and/or Venography **CPAP** = Continuous Positive Airway Pressure **CRP** = C-reactive protein **Day 0** = Day of Randomizations **DSMB** = Data Safety Monitoring Board **EPAP** = Expiratory Positive Airway Pressure **FACTT** = Fluid and Catheter Treatment Trial **FDA**=Food and drug administration **FiO**2 = Fraction of Inspired Oxygen **GCS** = Glasgow Coma Scale **HR** = Hazard Ratio **ICU** = Intensive care Unit **IFN-\alpha** = Interferon-gamma **IL-6** = Interleukin 6 **IMV** = Intermittent Mechanical Ventilation **IRB** = Institutional Review Board **IVRS** = Interactive Voice Response System

**MBW** = measured body weight MCP-1 = Monocyte chemotactic protein-1 **NF-\kappaB** = Nuclear factor kappa B **NHLBI** = National Heart Lung and Blood Institute **NIV**= Non-invasive ventilation **NOS**= Nitric oxide synthase **OR** = Odds Ratio **OI** = Oxygenation Index defined as mean airway pressure x  $F_10_2/Pa0_2$  $PaCO_2 = Partial pressure of arterial carbon$ dioxide  $PaO_2 = Partial pressure of arterial oxygen$ **PB** = Barometric Pressure **PBW** = Predicted Body Weight **PCV** = Pressure Control Ventilation **PEEP** = Positive End-Expiratory Pressure **PEG** = Percutaneous Endoscopic Gastrostomy **PIN** = Personal Identification Number **Pplat** = Plateau pressure **PS** = Pressure Support Ventilation **PAOP** = Pulmonary Artery Occlusion Pressure **RAGE** = receptor for advanced glycation end products **RCT** = Randomized Controlled Trial **SBT** = Spontaneous Breathing Trial **SIRS** = Systemic Inflammatory Response Syndrome **SOFA**=Sequential organ failure assessment  $SpO_2 = Oxygen Saturation$ **VFD** = Ventilator-free Day **VTE**= Venous thromboembolism **ULI** = Unilateral Lung Injury **ULN** = Upper limits of normal **VTE**=Venous thromboembolism; includes deep venous thrombosis and pulmonary thromboembolism **vWF** = von Willebrand factor

**LPS** = lipopolysaccharide

# DEFINITIONS

Acute Kidney Injury: Acute kidney injury network Stage 3 disease, defined as a threefold increase in creatinine from baseline or the need for dialysis

**Asian:** A person having origins in any of the original peoples of the Far East, Southeast Asia, or the Indian subcontinent including, for example, Cambodia, China, India, Japan, Korea, Malaysia, Pakistan, the Philippine Islands, Thailand, and Vietnam.

**Completing 48 hours of UAB (from weaning form)**: Defined as the date (calendar day) that the subject reaches exactly 48 hours of UAB. Example: if subject meets UAB at 1900 on 6/1/06 and does not return to AB, then the date of completing 48 hours of UAB would be 6/3/06.

**Date of first UAB (from Study Termination form)**: Defined as the first day that the subject is on UAB from midnight to midnight. Example: if subject meets UAB at 1900 on 6/1/06, then the date of first UAB would be 6/2/06, as long as subject does not return to AB on 6/2/06. **Extubation**: Removal of an orotracheal, nasotracheal tube, or unassisted breathing with a tracheostomy

**Home**: level of residence or health care facility where the patient was residing prior to hospital admission

**Hospital Mortality to Day 60:** This primary endpoint includes all deaths following randomization in any heath care facility prior to discharge "home" until study day 60. Study subjects still in a health care facility at study day 61 are considered alive for this endpoint.

**NYHA**: New York Heart Association Class IV subjects (defined as subjects who have cardiac disease resulting in inability to carry out physical activity without discomfort. Symptoms of cardiac insufficiency or an anginal syndrome may be present even at rest. If any physical activity is undertaken, discomfort is increased).

**Sepsis:** SIRS criteria plus suspected or known infection. Since intubation and hypoxemia is a requirement for enrollment into this trial, participants will, by definition, meet the respiratory SIRS criterion. They must also meet two of three non-respiratory SIRS criteria.

**Study hospital**: Defined as the hospital where the patient was randomized and enrolled. **Study withdrawal**: Defined as permanent withdrawal from study before completion of study activities. This does not include those subjects who have completed the protocol procedures or stopped procedures because they have reached unassisted breathing. If a patient or surrogate requests withdrawal from the study the clinician should seek explicit permission to continue data collection.

**UAB (Unassisted Breathing):** Spontaneously breathing with face mask, nasal prong oxygen, or room air, T-tube breathing, tracheostomy mask breathing, or  $CPAP \le 5$  without PS or IMV assistance, or the use of noninvasive ventilation solely for sleep-disordered breathing. Assisted breathing is any level of ventilatory support at pressures higher that the unassisted breathing thresholds.

# **Part I: Study Summary**

Title: Randomized Evaluation of Rosuvastatin for Acutely Injured Lungs from Sepsis

**Objective:** To assess the efficacy and safety of oral rosuvastatin in patients with sepsis-induced Acute Lung Injury (ALI).

Hypothesis: Rosuvastatin therapy will improve mortality in patients with sepsis-induced ALI.

### **Study Design:**

- 1. Multi-center, prospective, randomized, placebo-controlled clinical trial
- 2. A maximum of 1000 patients will be enrolled
- 3. Participants will be randomized to receive either rosuvastatin or placebo
- 4. Treatment will continue for 28 days, discharge from study hospital or death, whichever comes first.
- 5. All participants will be followed for 7 days following the last dose of study drug for adverse events. Participants will also be followed to the earlier of discharge home on UAB or day 60.

  - d. No clinical evidence of left atrial hypertension, or if measured, a Pulmonary Arterial Wedge Pressure (PAOP) less than or equal to 18 mm Hg. If a patient has a PAOP > 18 mmHg, then the other criteria must persist for more than 12 hours after the PAOP has declined to  $\leq$  18 mmHg, and still be within the 48-hour enrollment window.

"Acute onset" is defined as follows: the duration of the hypoxemia criterion (#1) and the chest radiograph criterion (#2) must be  $\leq 28$  days at the time of randomization. Opacities considered "consistent with pulmonary edema" include any patchy or diffuse opacities not fully explained by mass, atelectasis, or effusion or opacities known to be chronic (>28 days). The findings of vascular redistribution, indistinct vessels, and indistinct cardiac borders are not considered "consistent with pulmonary edema".

All ALI criteria (3a-d above) must occur within the same 24 hour period. The onset of ALI is when the last ALI criterion is met. Patients must be enrolled within 48 hours of ALI onset and no more than 7 days from the initiation of mechanical ventilation. SIRS criteria must occur within the 72 hours before ALI onset **and the 24 hours after ALI onset**. Information for determining when these time window criteria were met may come from either the Network hospital or a referring hospital reports.

#### **Exclusion Criteria:**

- 1. No consent/inability to obtain consent
- 2. Age less than 18 years
- 3. More than 7 days since initiation of mechanical ventilation (Example: If day of randomization is day "zero", date of current intubation cannot be prior to day "negative 7")
- 4. More than 48 hours since meeting ALI inclusion criteria
- 5. Patient, surrogate, or physician not committed to full support (Exception: a patient will not be excluded if he/she would receive all supportive care except for attempts at resuscitation from cardiac arrest)
- 6. Unable to receive or unlikely to absorb enteral study drug (e.g. patients with partial or complete mechanical bowel obstruction, intestinal ischemia, infarction, and short bowel syndrome)
- 7. Rosuvastatin specific exclusions
  - a. Receiving a statin medication within 48 hours of randomization
  - b. Allergy or intolerance to statins
  - c. Physician insistence on the use of or avoidance of statins during the ICU stay

- d. CK, ALT or AST > 5 times the upper limit of normal (ULN) except in patients with elevated CK who have an identifiable cause of CK elevation other than statin therapy providing the CK levels have fallen at least 10 % in the two most recent measurements and are less than 10 times ULN at randomization and the patient had not received any statins in the 30 days prior to enrollment (Example: A patient with staphylococcal sepsis has a CK of 3000 (10 times ULN). The next measurement is 2400 (8 times ULN). This patient would not be excluded for the elevated CK provided that no statins had been administered in the previous 30 days because the CK is now less than 10 times ULN, and the value has fallen more than 10% in the last two measurements).
  - i) If not available, a blood sample will be obtained after informed consent and results must be below protocol specified thresholds prior to randomization.
  - ii) CK, ALT and AST values obtained up to 24 hours prior to randomization are acceptable baseline values (e.g. Day zero) for both randomization and administration of the first dose of study.
- e. Diagnosis of hypothyroidism and not on thyroid replacement therapy
- f. Pregnancy or breast feeding
- g. Receiving niacin, fenofibrate, cyclosporine, gemfibrozil, lopinavir, ritonavir, atazanavir, daptomycin while on study drug
- 8. Severe chronic liver disease (Child-Pugh Score 12-15)
- 9. Moribund patient not expected to survive 24 hours
- 10. Chronic respiratory failure defined as  $PaCO_2 > 60$  mm Hg in the outpatient setting
- 11. Home mechanical ventilation (noninvasive ventilation or via tracheotomy) except for CPAP/BIPAP used solely for sleep-disordered breathing
- 12. Diffuse alveolar hemorrhage from vasculitis
- 13. Burns > 40% total body surface area
- 14. Interstitial lung disease of severity sufficient to require continuous home oxygen therapy
- 15. Unwillingness or inability to utilize the ARDS network 6 ml / kg PBW ventilation protocol
- 16. Cardiac disease classified as NYHA class IV
- 17. Myocardial infarction within past 6 months
- 18. Intraparenchymal Central Nervous System (CNS) bleed within a month of randomization.

Efficacy: The primary efficacy variable is Hospital Mortality to day 60.

#### Secondary Efficacy Variables:

- 1. Ventilator Free Days to day 28
- 2. Hospital mortality to day 28
- 3. Organ failure free days at day 14
- 4. ICU-free days at day 28
- 5. Hospital-free days at day 60

- 6. Increase in PaO2/FiO2 ratio and reduction in Oxygenation Index on study days 1-7 (to use ABGs as available)
- 7. Venous thromboembolism (VTE) to day 14
  - a. Documented by venous ultrasound, impedance plethysmography, contrast venography, ventilation-perfusion lung scan, CTPA/V, or pulmonary angiography
- 8. Composite end-point of myocardial infarction, bowel ischemia or ischemic stroke to study day 28
- 9. Arrhythmias during ICU stay or until day 14, whichever is first
- 10. Development of acute kidney injury (AKI)
- 11. Changes in plasma concentrations of CRP from day 0 to day 6 and day 14. Blood and urine will be reserved beyond study completion for additional biomarker studies.

**Focused Safety Analysis:** Incidence of elevations in CK > 10 times ULN or ALT > 8 times ULN as measured on days 0,1,3,6,14,21 (Appendix B)

**Study Drug Dosing:** All study drug doses will be administered via the enteric or oral route. Study drug will be blinded using an identical appearing placebo.

- 1. The first study drug dose (rosuvastatin or placebo) will be administered within 4 hours of randomization as a loading dose of 40 mg.
- 2. Subsequent doses will be at 10 am daily (+/- 4 hours) starting on the next calendar day as a maintenance dose of 20 mg.
  - a. If for any reason a maintenance dose is not administered at the intended time, it may be administered subsequently but not more than 12 hours after the intended time of administration.

Should the time be > 12 hours since last scheduled dose, the patient will not receive a dose on that study day but will be given a loading dose on the next calendar day. Maintenance dosing will continue on subsequent days.

Daily doses will be reduced by 50% for patients with a creatinine level of greater than or equal to 2.8 mg/dL who are not on renal replacement therapy. Loading doses will not be reduced.

Daily Dosing:

- Each subject will receive full dose if last known creatinine value is less than 2.8 mg/dL.
- Each subject will receive half dose if last known creatinine value is greater than or equal to 2.8 mg/dL (unless receiving renal replacement therapy in which case a full dose is given).

If used, antacids should be administered no closer than 6 hours before or after administering rosuvastatin to avoid affecting absorption of study drug. The dosage need not be adjusted for concomitant use of ketoconazole, erythromycin, itraconazole, fluconazole, warfarin or digoxin.

**Drug level specimens (venous blood):** The 40 mg loading dose and 20 mg maintenance dose are midrange doses and were selected based on the desire to quickly achieve and maintain plasma levels of rosuvastatin in the range of 10-70 ng/ml (see pharmacokinetic information

below). However, to verify adequate absorption of rosuvastatin, blood for peak and trough plasma rosuvastatin levels will be obtained on day 6 (+/- 2 days) in the first 60 patients and analyzed in the approximately 30 patients randomized to rosuvastatin. Trough levels will be drawn prior to the day 6 (+/- 2 day) dose. Peak levels will be drawn 3-5 hours after the dose.

The target plasma range for modifying lipid metabolism, as measured 3-5 hours after the day 6 (+/- 2 days) dose is expected to be between 10-70 ng/ml of rosuvastatin based on pharmacokinetic studies and reported half life of 10-20 hours. If mean plasma levels are lower than 10 ng/ml then the Steering Committee will consider increasing rosuvastatin loading and/or maintenance doses. If mean plasma levels are greater than 70 ng/ml, then the decision to modify the current dose will be based primarily on safety and early indications of efficacy. A formal recommendation regarding dose adjustments for high drug levels is not possible as the relationship, if any, of plasma levels to either the pleiotropic effects or the toxicities of statins is unknown. Dose changes will be recommended by the investigators and independently reviewed by the DSMB who will have unblinded access to the drug levels, adverse events, clinical and laboratory findings, and study outcomes.

**Completion of study drug administration:** Study drug administration will be stopped when one of the following conditions is met, whichever comes first:

- 1. 28 days after randomization or three days after ICU discharge (whichever occurs first)
- 2. Discharge from study hospital
- 3. Death

**Note:** If patient is readmitted to the ICU while still on study drug for three days after subsequent ICU discharge or day 28, whichever occurs first. If a patient is readmitted to the ICU after study drug has already been stopped per protocol, it does NOT get restarted when readmitted to the ICU.

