#### 3.3. Other Secondary Endpoints

- 1. Hospital mortality to day 28
- 2. Organ failure free days at day 14
- 3. ICU-free days at day 28
- 4. Hospital-free days at day 60
- 5. Increase in PaO2/FiO2 ratio and Oxygenation Index on study days 1-7

- 6. VTE at day 14
  - a) Documented by venous ultrasound, impedance plethysmography, contrast venography, ventilation-perfusion lung scan, CTPA/V, or pulmonary angiography
- Composite end-point of myocardial infarction, bowel ischemia or ischemic stroke to day 28
- 8. Arrhythmias during ICU stay or day 14, whichever is first
- 9. Development of acute kidney injury
- 10. Changes in plasma concentrations of CRP from day 0 to day 6 and 14. Blood and urine will be reserved beyond study completion for additional biomarker studies.

The rationale for the primary and first secondary endpoint is given in section 1.9. VTE is an endpoint because statins have been reported to be associated with lower rates of VTE in ambulatory patients. Cardiovascular endpoints are being assessed given the high prevalence of occult cardiovascular disease and the known benefits of statins in this population. The development of AKI is an endpoint as observational studies suggest statins prevent AKI. CRP is a surrogate marker of systemic inflammation and is expected to be reduced by statins.

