# 6.3. Assessments after Enrollment

The following data will provide the basis for assessing protocol compliance and safety as well as between-group differences in several efficacy variables. Data for each of the variables will be recorded on the days shown in the Time-Events schedule (Appendix F) or until death, discharge from the intensive care unit, or unassisted ventilation for 48 hours.

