#### **Reference Measurements**

The following parameters will be measured and recorded using values closest in time to 8:00 A.M. on the days specified in the Time-Events schedule (Appendix F). The following conditions will be ensured prior to measurements: no endobronchial suctioning for 10 minutes; no invasive procedures or ventilator changes for 30 minutes. All vascular pressures will be zero-referenced to the mid-axillary line with the patient supine.

- 1) If receiving assisted ventilation record daily up to day 7:
  - a) Tidal volume, FiO2, PEEP, inspiratory plateau pressure, and mean airway pressures
  - b) Pressure during inspiration if on a pressure targeted mode (PSV, PCV, etc).
  - c) Arterial PaO2, PaCO2, pH and SpO2
- 2) CK, AST, ALT as in schedule of events (Appendix F)
- 3) Fluid intake and output
- 4) Vital signs: Heart rate, systolic and diastolic blood pressure, body temperature, CVP
- 5) Modified Brussels Score data days 0-14:
  - a) Vasopressor use (Y/N), worst systolic BP, creatinine, bilirubin, and platelet count for the day. The date and value of the highest creatinine between days 15-28
- 6) CAM-ICU delirium screening assessment and RASS or RIKER sedation score through ICU discharge or study day 28 at select hospitals
- 7) Presence of myopathy
  - 8) Frontal Chest Radiograph Lung Injury Score
- 9) Occurrences of VTE, myocardial infarction, bowel ischemia, ischemic stroke and arrhythmias requiring treatment
- 10) Methylprednisolone equivalents greater than 20 mg
- 11) Daptomycin administration
- 12) Concomitant medications: niacin, fenofibrate, cyclosporine, gemfibrozil, lopinavir, ritonavir, or oral contraceptives. (Yes/No each day). The type and dose of statins prescribed as part of usual care if the study drug is withdrawn by the treating physician during the treatment period or prescribed after the treatment period will be recorded.
- a) Study drug/placebo will be stopped should one of these medications be started.
   13) Blood and urine for cytokines, mediators, and markers of inflammation. Plasma obtained from two, 10 ml EDTA anti-coagulated blood samples will be divided immediately after centrifugation into 4 equal 2 ml aliquots and frozen at -70°C. Urine obtained from the patients will be collected in an 8 ml sample tube and divided into 4 equal aliquots in specified tubes and frozen at -70°C. Specimens will be collected on days 3 and 6.
- 14) Plasma CRP levels on days 6 and 14

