### 6.5. Endpoint Determinations

- 1. Vital status at 60 days until discharged home on unassisted breathing.
- 2. Brussels Organ dysfunction failures at days 0-14
- 3. Time of initiation of unassisted breathing (assuming a patient achieves 48 consecutive hours of unassisted breathing)
- 4. Need for re-instituting assisted or mechanical ventilation after achieving 48 consecutive hours of unassisted breathing
- 5. Need for, timing, and duration of dialysis
- 6. Status 48 hours after initiation of unassisted breathing
- 7. ICU length of stay in calendar days including ICU days after readmission to ICU.
- 8. Hospital length of stay in calendar days and discharge disposition (home, other facility, with or without assisted ventilation)
- 9. For rosuvastatin toxicity:
  - a. CK > > 10 times ULN
  - b. ALT > 8 times ULN
  - c. AST > 8 times ULN

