# **APPENDIX F:** Time-Events Schedule

Measurement/Event	Day 0	1	2	3	4	5	6	7	8	9	10	12	14	21	28	60/ 90
Demographics, History & Physical, Height, Weight	Х															
AUDIT and smoking survey	Х															
Etiology of ARDS, site of sepsis	Х															
APACHE III Score	Х															
Brussels Score^	Х	X	х	х	Х	Х	Х	X	х	Х	Х	Х	Х			
GCS	Х							X					Х			
Ventilator Parameters (including FiO 2 ) *	Х	X	х	х	х			X				Х		X	х	
Arterial Blood Gases (PaO 2 , PaCO 2 , pH) and SpO 2	Х	A	A	А	A	А	А	Α					А	А	A	
Vital signs *	X	X	Х	Х	X	Х	X	X								
Blood Statin peak/trough level $^{\beta}$							Х									
Concomitant medications (Y/N)	Х	X	х	х	Х	Х	Х	X	Х	Х	Х					
Presence of myopathy €																
I/Os	Х	X	х	х	Х	Х	Х	X								
Occurrences of MI, VTE, ischemic stroke, bowel ischemia €																
Episodes of arrhythmias $^{\Omega}$	Х	X	Х	Х	Х	Х	Х	X	Х	Х	Х	Х	Х			
ALT β	Х	X	А	Х	А	А	Х	А	А	А	А	А	Х	X		
СК, β	Х	X	А	Х	А	А	Х	Α	А	Α	Х	А	Х	X		
AST	Х	х	А	х	А	А	х	А	А	Α	А	А	Х	Х		
Chest X-ray (LIS)	х	A	А	А	А	А	А	А	А	А	А					
Plasma CRP levels $^{\beta}$	Х						Х						Х			
Blood for DNA	Х															
Blood and Urine for markers of inflammation $^{\beta}$	Х			Х			х									
Study Drug Administration Record	Х	X	х	Х	х	Х	х	X	Х	Х	Х	Х	Х	X	х	
Vital Status															X	Х

X = Required

A=When available

\*Data gathered at times indicated or until patient achieves 48 hrs of unassisted breathing, whichever is sooner

€ Data gathered until 72 hours after study drug is discontinued

^Daily for 14 days or until ICU discharge and the date and value of the highest creatinine between day 15 and 28

 $^{\Omega}$  Data gathered until day 14 or ICU discharge, whichever occurs first

β These may be obtained plus or minus two days except for baseline and day 1. Attempt to maintain spacing between labs and samples if obtaining on days other than those specified.

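### The protocol gives conflicting stop rules for recording creatinine; if Appendix F is followed, some non-dialysis AKI between ICU discharge and day 15 is never captured

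*Protocol*

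**What the plan says.** AKI is item 10 of the secondary efficacy variables in Part I, "Development of acute kidney injury (AKI"), and item 9 in section 3.3 ("Development of acute kidney injury"). Neither place gives an end day. Neighbouring items do have one, for example "Venous thromboembolism (VTE) to day 14". The Definitions section gives two routes to the endpoint, again without a window: "Acute kidney injury network Stage 3 disease, defined as a threefold increase in creatinine from baseline or the need for dialysis".

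The two routes are collected differently.

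- **Dialysis.** Section 6.5 item 5 records "Need for, timing, and duration of dialysis", with no limit at ICU discharge.
- **Creatinine.** It is part of the Brussels data. The Appendix F footnote to that row reads "Daily for 14 days or until ICU discharge and the date and value of the highest creatinine between day 15 and 28". The lead-in to section 6.3 says data are recorded on the Appendix F days or "until death, discharge from the intensive care unit, or unassisted ventilation for 48 hours".

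Two other places point to longer recording. Section 3.4 follows patients for organ failure until death, hospital discharge or day 14, whichever is first. Section 6.3 item 5 sets days 0-14 for the Brussels data without an ICU limit of its own, and then adds: "The date and value of the highest creatinine between days 15-28".

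**The concern.** A site working from Appendix F would stop abstracting creatinine when the patient leaves the ICU and would take it up again on day 15. A site working from section 3.4 would continue on the ward. The same patient could be scored differently under the two rules, and no analysis plan can later recover values that were not collected.

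The gap also opens at a post-randomization event that treatment is meant to bring forward: ICU-free days and ventilator-free days are themselves efficacy variables. Section 3.3 lists AKI because observational studies suggest that statins prevent it. A collection rule that observes faster-recovering patients for less time would lean in the direction of that hypothesis.

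**Working it through.** The protocol states no AKI rate, AKI power or ICU length of stay, so there is no figure of its own to reproduce. The check has three steps.

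**1. The stop rules side by side**

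| Place | Creatinine recorded until | Gap between ICU discharge and day 15? |
|---|---|---|
| Section 3.4 | death, hospital discharge or day 14 | none while in hospital |
| Section 6.3 item 5 | day 14, then highest value for days 15-28 | none |
| Section 6.3 lead-in | Appendix F days, or death, ICU discharge or 48 h unassisted ventilation | yes |
| Appendix F, Brussels footnote | day 14 or ICU discharge, then highest value for days 15-28 | yes |

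The 48-hour limit should carry little weight for creatinine. In Appendix F it is a separate footnote attached to ventilator parameters and vital signs. The Brussels row has its own footnote, which does not mention it. The lead-in also cannot govern every item literally, because items 5 and 6 beneath it run to day 28.

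**2. What is lost under the Appendix F rule**

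For ICU discharge on day D, the unrecorded stretch is max(0, 14 − D) days:

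- D = 5: 9 days
- D = 7: 7 days
- D = 9: 5 days
- D = 11: 3 days
- D = 14: 0 days

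Each day of earlier discharge adds one day. An AKI episode starting in that stretch is still counted if the patient is dialysed (section 6.5), or if creatinine remains threefold raised on or after day 15 and is measured (the day 15-28 maximum). It is lost only if there is no dialysis and it resolves, or is followed by death or hospital discharge, before day 15.

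**3. Possible size of an imbalance between arms**

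All inputs here are assumptions. Only the 2.25 days appears in the protocol, as the design difference in ventilator-free days (section 7.2); it is borrowed as a shift in ICU discharge.

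*Fixed discharge day.* A share s of patients leaves the ICU alive on day D (control) or D − 2.25 (faster arm). The daily hazard h of non-dialysis AKI after discharge is the same in both arms, and every gap episode is lost.

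- Missed proportion = s × (1 − exp(−h × gap)).
- Low end: h = 0.25%, s = 0.3, D = 7, gaps 9.25 and 7 days. Difference = 0.3 × (e^−0.0175 − e^−0.0231) = 0.17 points.
- High end: h = 1%, s = 0.7, D = 11, gaps 5.25 and 3 days. Difference = 0.7 × (e^−0.03 − e^−0.0525) = 1.51 points.

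*Exponential ICU stay.* Mean stay m is 10 days (control) or 8 days (faster arm), with h = 1% per day in the ICU and afterwards, and no deaths or hospital discharges.

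- Mean gap = 14 − m(1 − e^(−14/m)): 6.5 and 7.4 days.
- True AKI to day 14 = 1 − e^−0.14 = 13.1% in both arms.
- Recorded if all gap episodes resolve = [h/(h + 1/m)] × [1 − e^(−14(h + 1/m))]: 7.14% and 6.29%, a difference of 0.85 points.
- Recorded if half of the gap episodes persist to day 15: 10.10% and 9.68%, a difference of 0.43 points (0.427 before rounding).

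For scale, with 500 patients per arm (1000 split equally) and recorded AKI of 7% to 10%, the standard error of the difference is √(2p(1 − p)/500), or 1.6 to 1.9 points. The bias in the exponential model is therefore about 0.2 to 0.5 standard errors.

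**The case against.** The strongest reply is that section 3.4 and section 6.3 item 5, read together, give creatinine throughout the hospital stay to day 28, so no gap exists and Appendix F is only loosely worded. This stands in part: the protocol does not settle that creatinine goes unrecorded after ICU discharge. But Appendix F is the schedule to which section 6.3 sends the sites, and its footnote names ICU discharge explicitly. The contradiction is real, and it matters which rule is used.

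A second reply is that the missing end day for AKI is minor. The collection windows already point to day 28, and an analysis plan commonly fixes such a window. That is accepted; the weight here lies on what is collected. It is also fair to note that arrhythmias in the same list are bounded by ICU stay on purpose. For AKI, however, resuming creatinine on days 15-28 shows that ICU discharge was not meant to end observation.

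A reader might infer stronger things that the documents do not support:

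- *All AKI after ICU discharge is missed.* Dialysis and persisting rises are captured.
- *The 48-hour unassisted-breathing limit widens the gap.* Appendix F attaches that limit to other rows.
- *A drug that merely shortens ICU stay will appear to prevent AKI.* The imbalance requires ICU discharge to differ by arm, and its size rests wholly on assumed inputs. One of these, in the exponential model, is a ward hazard as high as the ICU hazard, which is probably generous for patients well enough to leave.

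**Conclusion.** The point holds as a contradiction in the data-collection rules with a foreseeable consequence for a secondary endpoint. Sections 3.4 and 6.3 item 5 cannot both be followed together with Appendix F and the section 6.3 lead-in. If Appendix F prevails, a limited class of true events is lost in both arms, which costs some power whether or not the arms differ in ICU stay.

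If one arm leaves the ICU earlier, recorded AKI in that arm is biased downward. The direction follows from the rule, given equal post-ICU risk. The size cannot be derived from the protocol: it is 0.2 to 1.5 points over the assumed ranges, and probably towards the lower part, since the models treat most or all gap episodes as lost and ignore death and hospital discharge. That is under one standard error of the AKI comparison. The primary endpoint is not affected. The change is worth making because it is cheap and because the gap cannot be filled afterwards.

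**What to change.** 1. Use one creatinine stop rule, worded alike in section 3.4, the section 6.3 lead-in, section 6.3 item 5 and the Appendix F footnote. It should not depend on ICU discharge or unassisted breathing.
2. Start the existing item for the date and value of the highest creatinine on the day that daily recording ends, instead of on day 15, and run it to day 28 while the patient is in hospital. Routine values suffice.
3. State the endpoint as AKI to day 28 in Part I item 10 and section 3.3 item 9, and count dialysis over the same window.
4. Acknowledge that creatinine after hospital discharge remains unobserved. Hospital discharge is also a post-randomization event, so this narrows the recovery-dependent gap but does not abolish it.

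The cost is wording changes in five places (Part I, 3.3, 3.4, 6.3 and Appendix F), an earlier start for one case report form item, and slightly more chart abstraction on the ward. No new blood draws are needed.
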